5.3 DOSE ESCALATION RULES

The sponsor will review safety data for all patients after the last patient in Group A has completed the week 4 visit or discontinued for any reason other than DLT. The sponsor will initiate escalation to the Group B dosing cohort after confirmation that no safety signals are identified and no study stopping rules have been met.

The National Cancer Institute Common Terminology Criteria for Adverse Events (NCI-CTCAE) v4.03 will be used to grade the severity of adverse events.

- Any AE (with the exception of worsening AD symptoms or injection site reactions) of grade 2 or higher that is probably or definitely related to study drug must be reported to the sponsor within 24 hours of learning of the event.
- Any grade 3 or greater injection site reaction must be reported to the sponsor within 24 hours of learning of the event.
- If three or more probably or definitely related grade 2 or greater AEs, and/or three or more grade 3 or greater injection site reactions occur in either group, dosing will be stopped for safety assessment.

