7. ASSESSMENT OF SAFETY

Safety will be assessed by monitoring adverse events, vital signs, physical examinations, ECG and clinical laboratory measurements. All subjects who have received at least one dose of bermekimab will be included in the safety analysis. Adverse events will be monitored from Visit 1 (post-infusion) to Visit 9. Any serious adverse events or grade 2 or greater probably or definitely related events will be followed until resolution.

Study drug will be administered under close observation in a facility equipped to handle anaphylaxis. Subjects must be closely monitored until at least 1 hour following the administration of the antibody or 1 hour after their vital signs have stabilized.

Any AE (with the exception of worsening AD symptoms or injection site reactions) of grade 2 or higher must be reported to the sponsor within 24 hours of learning of the event. Any grade 3 or greater injection site reaction must be reported to the sponsor within 24 hours of learning of the event.

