9. ADVERSE EVENTS

9.1 DEFINITION OF ADVERSE EVENT (AE)

An adverse event is defined as any untoward medical occurrence in a subject participating in a clinical study that does not necessarily have a causal relationship with the pharmaceutical or biological agent under study. An AE can therefore be any of the following:

- Any unfavorable and unintended sign (including laboratory findings), symptom, or disease temporally associated with the use of bermekimab, whether or not it is apparently related to bermekimab
- A concurrent illness
- An exacerbation, or an unexpected increase in frequency or intensity of a preexisting condition, including intermittent or episodic conditions. However, anticipated day-to-day fluctuations or expected progression of the preexisting condition (based upon the Investigator's clinical judgment) are not to be considered AEs
- A significant or unexpected worsening of the condition/indication under investigation. However, anticipated day-to-day fluctuations or expected progression of the disease under investigation (based upon the Investigator's clinical judgment) are not to be considered AEs
- A suspected interaction between the investigational drug and concomitant medications
- Any clinically significant laboratory abnormality (including radiological interpretations, histopathological findings, etc.)

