9.6 REPORTING REQUIREMENTS

Any AE (with the exception of worsening AD symptoms or injection site reactions) of grade 2 or higher must be entered into the eCRF within 24 hours of learning of the event. Any grade 3 or greater injection site reaction must be reported to the sponsor within 24 hours of learning of the event.

All serious adverse events (SAEs) should be reported to the Sponsor within 24 hours of knowledge of the event. These immediate reports should be followed promptly by detailed, written reports. The subject should be followed up with until stabilization of the reported SAE, either with full satisfactory resolution or resolution with sequelae, or until death of the subject. Before declaring the subject is lost to follow-up, three unsuccessful attempts at contact should be made and recorded on the SAE form. The immediate and follow-up reports should identify subjects by unique code numbers assigned to the trial subjects rather than by the subjects' names, personal identification numbers, and/or addresses. The Investigator should also submit SAEs to the IRB/EC according to their IRB/EC guidelines [ICH-GCP E6]. Drug-related Serious Adverse Events will be reported to the FDA by XBiotech's Medical Safety Officer according to 21 CFR 312.32.

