11.8 CASE REPORT FORMS

Data for this protocol will be captured electronically in an Electronic Data Capture (EDC) system. Designated study personnel will be provided unique user names and passwords. Each study personnel will have specific access within the electronic data collection system based on their role. The EDC system contains an audit trail associated with each individual's unique password that will document date and time of data entry and revisions. All protocol-specified data is to be entered into the EDC system in a timely manner for review and audit by XBiotech. All data is to be entered such that it will allow accurate interpretation and tabulation. It is the Investigator's responsibility to ensure that all discontinued orders or changes in study or other medications entered into the database correspond to entries in the subject's medical records (i.e. source documents) and to acknowledge accurate completion of the eCRF.

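### Read literally, the three-event dosing stop in 5.3 counts related worsening AD and related grade 2 injection site reactions, but no timed report brings these events to the sponsor unless they are serious

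*Combined protocol and SAP*

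**What the plan says.** The third bullet of 5.3 (Dose Escalation Rules) is the group dosing stop. Dosing halts for a safety assessment "If three or more probably or definitely related grade 2 or greater AEs, and/or three or more grade 3 or greater injection site reactions" are seen in either group. Its AE limb names no exception.

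Under 9.1, AEs include "A significant or unexpected worsening of the condition/indication under investigation"; anticipated fluctuation and expected progression are left out.

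The expedited-reporting text is narrower than the stop:

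- 5.3, first bullet, puts drug-related events on a 24-hour report to the sponsor: "Any AE (with the exception of worsening AD symptoms or injection site reactions) of grade 2 or higher that is probably or definitely related".
- Section 7 has "Any AE (with the exception of worsening AD symptoms or injection site reactions) of grade 2 or higher must be reported to the sponsor" on the same clock.
- 9.6 sets a 24-hour limit for data entry: "Any AE (with the exception of worsening AD symptoms or injection site reactions) of grade 2 or higher must be entered into the eCRF".
- Injection site reactions have a 24-hour report only from grade 3 (5.3, 7 and 9.6).

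Two provisions cover what is left. Serious events come back in: "All serious adverse events (SAEs) should be reported to the Sponsor within 24 hours of knowledge of the event". For everything else, 11.8 says "All protocol-specified data is to be entered into the EDC system in a timely manner", with no number of days.

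Section 5.5, on stopping treatment in an individual patient, writes the AD and injection-site exception out in full.

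**The concern.** A stopping rule works only if the party applying it learns of every event it counts. The study is multicenter, so three qualifying events may occur at three sites, and only the sponsor can add them up. Dosing is weekly. If the third event is a non-serious related AD flare, or a related grade 2 injection site reaction, no deadline ensures that the sponsor knows of it before the next round of injections. Safety and tolerability is the primary endpoint, and AD is the disease under treatment, so flares are a foreseeable kind of event.

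The wording also leaves room for two practices. A reader who carries the first bullet's exception into the third would never count a related AD flare towards the stop; a reader who takes the third bullet as it stands would count each one from grade 2.

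**Working it through.** **Step 1: what the stop counts and what is reported within 24 hours.** All events below are probably or definitely related and non-serious.

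| Event | Counts under 5.3 bullet 3, as written | 24-hour route |
|---|---|---|
| Grade 2 or greater AE, neither AD nor injection site | Yes | Yes |
| Grade 2 or greater worsening AD that meets 9.1 | Yes | No, at any grade |
| Grade 2 injection site reaction | Yes | No |
| Grade 3 or greater injection site reaction | Yes | Yes |

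Rows 2 and 3 are the mismatch. Three row 2 events meet the stop with 0 of 3 expedited reports. Two row 1 events plus one row 2 event meet it with 2 of 3. Neither count needs an assumed rate.

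**Step 2: exposure per week of delay.** Group A has 9 patients at 200 mg weekly and Group B has 20 at 400 mg weekly (synopsis). Each week of delay allows at most 9 or 20 further injections, and only if the whole cohort is on treatment at once.

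**Step 3: how much the reading matters.** The plan gives no operating characteristics for the stop, so there is no figure to reproduce. The rates here are assumptions. Let X ~ Bin(n, 0.05) be patients with another related grade 2 or greater AE. Let Y ~ Bin(n, r) be patients with non-serious related grade 2 or greater worsening AD. X and Y are independent, with one event per patient per type.

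Group B, AD not counted: P(X ≥ 3) = 1 − (0.95^20 + 20 × 0.05 × 0.95^19 + 190 × 0.05² × 0.95^18) = 1 − (0.3585 + 0.3774 + 0.1887) = 7.5%, or 7.55% before rounding of the terms (7.6% below).

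Group B, AD counted, r = 0.05: X + Y ~ Bin(40, 0.05), so P(X + Y ≥ 3) = 1 − (0.95^40 + 40 × 0.05 × 0.95^39 + 780 × 0.05² × 0.95^38) = 1 − (0.1285 + 0.2706 + 0.2777) = 32.3%.

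| Assumed r | A (n=9): AD not counted | A: AD counted | B (n=20): AD not counted | B: AD counted |
|---|---|---|---|---|
| 2% | 0.8% | 2.3% | 7.6% | 16.3% |
| 5% | 0.8% | 5.8% | 7.6% | 32.3% |
| 10% | 0.8% | 14.7% | 7.6% | 58.7% |

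If each patient can contribute only one counted event, the rate becomes 1 − 0.95 × (1 − r), and the Group B figures with AD counted are 15.6%, 30.9% and 57.0%. The picture is the same.

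**Step 4: injection site reactions.** Section 9.7 reports 20 of 831 patients (2.4%) with injection site or infusion reactions, across mixed routes. Using that for all grades, Bin(n, 20/831) gives P(≥ 3) = 0.1% for n = 9 and 1.2% for n = 20. This part of the mismatch is minor.

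**The case against.** The strongest reply is that the third bullet was never meant to count AD. The first two bullets of 5.3 set up two categories, related grade 2 or greater AEs other than AD and injection site reactions, and grade 3 or greater injection site reactions. The third bullet counts to three over what look like the same two. If its AE limb already took in injection site reactions, the separate injection-site limb would add only those not judged related and would be almost redundant. Section 5.5 uses the same pair with the exception written out. On this reading the count and the reports agree, and only a cross-reference is missing. That stands as an equally plausible intention. Section 7 does not settle it: "Any serious adverse events or grade 2 or greater probably or definitely related events will be followed until resolution" omits the exception, but it governs follow-up and not what counts towards a stop.

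Three more points stand in part.

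- AEs are collected at weekly visits and entered in the EDC system. A reader might infer that the count cannot be kept promptly. The documents show only that no deadline ensures it.
- Few events are likely to qualify. They must go beyond expected fluctuation or progression (9.1) and be judged probably or definitely drug-related after natural history is considered (9.5).
- Other safeguards exist. Section 5.6 suspends enrollment for two or more related SAEs, or for a significant related finding in the investigator's opinion. Systemic rescue ends treatment (5.4, 5.5), and 5.5 lets the investigator stop a patient. Escalation to Group B requires that no safety signal is found and no stopping rule is met. None of these keeps the third bullet's count of non-serious events while dosing continues, and 5.3 states no scheduled sponsor review once Group B has started.

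**Conclusion.** The mismatch is real on the text. The stop as written counts two kinds of event that the 24-hour provisions leave out, and no timed route ensures that the sponsor can act on them before the next weekly dose. Which way to resolve it is not certain, because the exception may have been meant to carry over. The affected events are probably few, and this is a modest correction to a safety rule.

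The probabilities show only how far the choice of reading moves the chance of a pause, and they rest on assumed rates and independence. A reader might take the difference between the columns (for Group B at r = 5%, 32.3% − 7.6%, about 25 percentage points) as the chance of a late stop. It is not: it includes every case with fewer than three expedited reports, even if the AD event is entered the next day, and no entry delay is modelled. Nor do the documents support the inference that the sponsor definitely intended AD flares to count.

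**What to change.** 1. Add one sentence to 5.3, section 7 and 9.6: *Worsening AD that meets the definition in 9.1, is grade 2 or greater and is probably or definitely related to study drug must also be reported to the sponsor within 24 hours of learning of the event.* Do not raise this to grade 3 while the stop counts from grade 2, since that would leave the gap open. This sentence is worth adding whichever reading was intended.
2. Have the sponsor state in the third bullet of 5.3 whether worsening AD and related grade 2 injection site reactions count. Either keep both in the count and give both a matching 24-hour report, or repeat the first bullet's exception there.

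The individual rules in 5.4 and 5.5 can stay, so patients on topical rescue may continue treatment. The sponsor should know, however, that counting AD could pause a whole group for events that 5.5 exempts from its related-AE stop for the individual patient.

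The cost is a few lines of text, with no new visits or patients. For AD, expect 29 × 0.02 = 0.58, 29 × 0.05 = 1.45 or 29 × 0.10 = 2.9 extra expedited reports at the assumed rates, one per patient. If AD is counted, the price is a higher chance of a group pause than under the carried-over reading, for example 32.3% against 7.6% in Group B at the assumed 5% rates.

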5.4 RESCUE TREATMENT(S)

If medically necessary (ie, to control intolerable AD symptoms), rescue treatment for AD may be provided to study patients at the discretion of the investigator. For the purpose of efficacy analysis, patients who receive rescue treatment during the study treatment period will be considered treatment failures, but they will continue study treatment if rescue consisted of topical medications. Topical calcineurin inhibitors may be used for rescue, but should be reserved for problem areas only, eg, face, neck, intertriginous and genital areas, etc. If possible, investigators should attempt to limit the first step of rescue therapy to topical medications, and escalate to systemic medications only for patients who do not respond adequately after at least 7 days of topical treatment. If a patient receives rescue treatment with systemic corticosteroids or non-steroidal systemic

immunosuppressive drugs (cyclosporine, methotrexate, mycophenolate-mofetil, azathioprine, etc.) study treatment will be immediately discontinued. Investigators should make every attempt to conduct efficacy and safety assessments (eg, disease severity scores, safety labs) immediately before administering any rescue treatment.

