10. STATISTICAL PLAN

This section provides the basis for the statistical analysis plan (SAP) for the study. The SAP may be revised during the study to accommodate amendments to the clinical study protocol, and to make changes to adapt to unexpected issues in study execution and data that may affect planned analyses. Analysis variables are listed in Section 8.

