10.3 ANALYSIS SETS

10.3.1 Safety Analysis Sets

The safety analysis set (SAF) consists of all patients that receive at least one dose of study medication and will be analyzed as treated.

The secondary endpoints will be analyzed based upon the SAF, as well as the per protocol population (PP). The per protocol population will consist of those patients that complete both the baseline and visit 8 assessments of their atopic disease (as specified for the secondary endpoints).

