10.5.1 Handling Missing Data

If baseline assessment is not available, the baseline value will remain missing. The subject will not be included in baseline summaries.

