10.5.4 Efficacy Analysis

All primary and secondary efficacy analyses will be performed for SAF and PP populations. Summary statistics will be provided to evaluate the overall treatment effect and effect within the treatment group. No statistical comparison of differences will be performed across bermekimab dose groups.

Change from baseline to visit 8 will be summarized using descriptive statistics. Corresponding 95% confidence interval of the point estimate of mean change will be provided by treatment group and for overall pooled population. The number and percent of subjects achieving the response (as specified for the secondary endpoints) will be summarized by treatment groups and overall population along with 95% confidence interval for the point estimate. Number and percent of patients achieving response in EASI, and SCORAD core from baseline at visit 8, will be reported separately, along with 95% confidence interval for 50% or greater reduction.

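### Section 5.4 counts any rescued patient as a failure, but the IGA rule in 3.1 needs more than one added treatment and 10.5.4 lets post-rescue visit 8 scores into the Group B mean changes

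*Combined protocol and SAP*

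**What the plan says.** Section 5.4 sets the rescue rule for efficacy analysis: "patients who receive rescue treatment during the study treatment period will be considered treatment failures". Failing in this sense does not by itself stop dosing, as the section goes on to say of these patients: "but they will continue study treatment if rescue consisted of topical medications". Systemic rescue ends study drug. The section also gives a data-collection instruction: "Investigators should make every attempt to conduct efficacy and safety assessments (eg, disease severity scores, safety labs) immediately before administering any rescue treatment". It does not say what those pre-rescue scores are for.

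Section 3.1 has its own trigger under the IGA 0/1 endpoint. A patient given more than one additional treatment for an AD exacerbation, or with no visit 8 IGA, is a non-responder. No other endpoint in 3.1 mentions added AD medication.

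Section 10 opens with "This section provides the basis for the statistical analysis plan (SAP) for the study". Within it:
- 10.5.4, responder endpoints: "The number and percent of subjects achieving the response (as specified for the secondary endpoints) will be summarized".
- 10.5.4, change endpoints: "Change from baseline to visit 8 will be summarized using descriptive statistics", with a 95% CI for the mean change.
- 10.3.1: "The per protocol population will consist of those patients that complete both the baseline and visit 8 assessments of their atopic disease".
- 10.5.1: "If baseline assessment is not available, the baseline value will remain missing".

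None of these mentions rescue or refers back to 5.4.

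**The concern.** A failure label settles a yes/no endpoint but gives no number for a change score. Topically rescued patients stay on study drug and are scored at visit 8, so the plan foresees the case without saying how to analyse it. The same patient could be a failure for EASI-50 and an improver in the mean EASI change.

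The comparison is also uneven. Section 4.2 keeps patients off topical corticosteroids (TCS) and topical calcineurin inhibitors (TCI) for the week before baseline, so a rescued patient's change can set an off-topical score against an on-topical one. There is no control arm in which the same effect would appear. Section 1.2 says the study is to support later randomized trials, so the Group B mean changes may be used in planning them.

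On IGA 0/1, the two sections give different answers for a patient rescued exactly once, and 10.5.4 points to the endpoint definitions without mentioning 5.4.

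**Working it through.** The plan states no figure to reproduce: Section 10.2 calls the sample one of convenience.

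**1. Endpoints touched (Section 3.1).** There are 14 secondary endpoints. PK and the Visit 1 Questionnaire are not visit 8 efficacy endpoints, so 14 − 2 = 12. Four are responder endpoints (IGA 0/1, IGA reduction of 2 or more, EASI-50, SCORAD-50). That leaves 12 − 4 = 8 changes to visit 8: EASI, two NRS, SCORAD, POEM, GISS, DLQI and HADS.

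**2. Group affected.** Section 3 ends Group A follow-up at visit 6. Only Group B (planned n = 20) has visit 8 scores, and the pooled visit 8 summary rests on the same patients.

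**3. Path of a topically rescued patient.** Section 5.4 keeps the patient on drug. Section 2.9.1 prohibits TCS and TCI but leaves them off the list that stops study drug. The patient is scored at visit 8, belongs to the SAF (at least one dose), and meets the PP definition (baseline and visit 8 assessed). Nothing in 10.5.4 removes or replaces the score.

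**4. IGA 0/1, patient rescued once with a visit 8 IGA of 0 or 1.** Section 5.4 gives failure. Section 3.1 gives responder.

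**5. Illustrative shift in mean EASI change.** Shift = k × g / n, where k is the number rescued, g the points gained between the pre-rescue score and visit 8, and n the number scored at visit 8. All values of k and g, and n = 16, are assumptions.

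| k | g | n = 20 | n = 16 |
|---|---|---|---|
| 1 | 4 | 0.20 | 0.25 |
| 2 | 4 | 0.40 | 0.50 |
| 4 | 4 | 0.80 | 1.00 |
| 1 | 8 | 0.40 | 0.50 |
| 2 | 8 | 0.80 | 1.00 |
| 4 | 8 | 1.60 | 2.00 |

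Against the minimum entry EASI of 16 (Section 4.1), 0.20/16 = 1.25% and 2.00/16 = 12.5%; the share is smaller if mean baseline is higher. This is not an upper limit. If rescued patients were instead set to no change, 1 to 6 rescued with observed improvements of 8 to 16 points would shift the mean by 1 × 8/20 = 0.4 to 6 × 16/20 = 4.8 points. The inputs drive the result.

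**6. Illustrative IGA effect, if 3.1 is applied without 5.4.** Each once-rescued responder moves the Group B SAF rate by 1/20 = 5 percentage points. The denominator stays at 20 because a missing visit 8 IGA counts as non-response. With 6 responders assumed, one of them rescued once: 6/20 = 30% (exact 95% CI 11.9 to 54.3) against 5/20 = 25% (8.7 to 49.1). In PP with 16 scored, the step is 1/16 = 6.25 points.

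**The case against.** A reader might infer that summarising the observed visit 8 score breaches 5.4. It does not. Section 5.4 assigns no change value, failure is naturally a responder label, and using scores regardless of rescue is a recognised choice. The problem is that the plan arrives at it by silence.

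A reader might also infer that no rescue rule exists anywhere. The documents do not show that. Section 10 is described as the basis for a SAP, no separate SAP is in the file, and it may contain a rule.

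On IGA, 5.4 covers efficacy analysis generally and can be applied on top of 3.1 as the stricter rule. The 5-point step then disappears. This stands, but 10.5.4 directs the analyst to the endpoint definitions and does not mention 5.4, so the result depends on which section is followed.

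The sizes are wholly assumed. TCS and TCI are otherwise prohibited through visit 9, and rescue is reserved for medical necessity, so few patients may be rescued. This stands too.

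Replacing later scores with pre-rescue ones is one choice among several, and without a control arm neither summary isolates the drug effect. That is a reason to report both.

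**Conclusion.** The point holds in two parts. The failure rules in 5.4 and 3.1 disagree for a patient rescued exactly once. And under 10.5.4 as written, post-rescue Group B scores enter 8 of the 12 visit 8 endpoints, in both SAF and PP.

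Improvement can be overstated if at least one patient is topically rescued before the visit 8 assessment and scores better afterwards. The documents do not support a claim that results are biased by a known amount.

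Nor does the point reach the safety primary endpoint, dose escalation or the stopping rules, none of which uses these summaries. No hypothesis is tested on the primary endpoint and dose groups are not compared. Low priority, worth settling because it is cheap and because a rule chosen after seeing open-label scores could be driven by them.

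**What to change.** - **Section 3.1:** count any rescue as in 5.4 as IGA 0/1 non-response.
- **Definition:** rescue means TCS, TCI, or a systemic corticosteroid or immunosuppressant given for AD, flagged in the CRF. Section 2.9.2 permits antihistamines, topical anesthetics and anti-infectives, so a concomitant medication record alone does not identify rescue.
- **Section 10.5.4 or the SAP:** report each Group B change endpoint (a) as observed and (b) with values after first rescue replaced by the last assessment before it. Use the 5.4 pre-rescue score if taken; otherwise the last scheduled visit or, for NRS, the last completed weekly diary average; otherwise a change of 0 from the visit 1 baseline defined in 8.1. State N for each summary and the number rescued.
- **Scope of (b):** limit it to patients with a visit 8 score, or state plainly that rescued dropouts are imputed while other dropouts are not. Create no visit 8 values for Group A.

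Cost: a few sentences, one wording change, one CRF flag and one extra table. When and how rescue is given does not change, and no new assessments are needed: Section 5.2 schedules these scales at every visit from 1 to 9. With visit windows of ±2 days, the last scheduled score is at most 7 + 2 + 2 = 11 days old, or 14 + 2 + 2 = 18 if one visit is missed.

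Downsides: reported improvement may be smaller, and single imputation treats a filled-in value as observed and makes the CI too narrow, hence both summaries.
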